11.2. Study Periods

See [Table 2](#) in [Section 29](#) for the schedule of procedures and assessments across the time points for the study.

11.2.1. Clinic Visit 1: Day 1 (Screening/Baseline) and up to Day -3 (Additional Screening Days, If Needed)

Subjects will visit the clinic site for their Screening/Baseline visit (Visit 1, -3 to 0 days) and undergo screening processes for entry into the study. Subjects who meet the inclusion and no exclusion criteria will be entered into the study.

The following screening assessments will be conducted by the Investigator or designee prior to subject enrollment. If needed, the following screening assessments may be completed within 3 days prior to Day 1 (-3 to 0 days):

- Informed consent to be signed
- A urine pregnancy test for all females of childbearing potential
- Medical history and demographic data, including sex, age, race, ethnicity, body weight (kg), height (cm), body mass index (BMI) (kg/m^2), and smoking habits
- Physical examination
- Neurological examination
- The alcohol breathalyzer and urine drug screen
- Laboratory tests (serum chemistry, hematology, and urinalysis)
 - blood sample for DNA genotyping for CYP450 2D6 polymorphism would be collected at same time of other required blood draw
- Vital signs (supine and standing blood pressure [including orthostatic pressure], sitting heart rate (after approximately 3 minutes at rest), respiratory rate, and body temperature,)
- A 12-lead ECG
- Prior and/or concomitant medications during the study will be recorded, as well as those that qualify as rescue medications (see [Section 12.8](#))
- Inclusion/exclusion criteria to be reviewed for qualification of the subject's enrollment into the study

The following baseline assessments will be conducted by the Investigator or designee prior to dosing on Day 1. If any screening assessments were completed prior to Day 1, inclusion/exclusion criteria are to be re-reviewed for qualification of the subject's enrollment into the study:

- Baseline assessments for study efficacy endpoints:
 - Subject rating of pain “right now” (NRS), must be 4 or greater

- Global severity of pain assessment by the physician and the subject on a scale of 1-5, with 1=none, 2=mild, 3=moderate, 4=severe, 5=very severe
- Functionality assessment:
 - Fingers to Floor Distance (FFD)
- Disability assessment:
 - Oswestry Pain and Disability Index (ODI) via the site study-provisioned tablet

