12. STUDY PROCEDURES

12.1. Numerical Rating Scale to Assess Subject's Pain Level due to Muscle Spasm

The NRS is a scale of 0 to 10 (0=no pain, 10=worst possible pain). Subjects will use the NRS to evaluate their pain ("right now") on Day 1 (baseline assessment) and on Days 4 (Visit 2) and 14 (Visit 3) during the clinic visit via the site study-provisioned tablet.

In addition, the NRS scale will be used by subjects for pain assessment at rest and upon movement in the evening (8–10 pm) on Days 1 to 14 recorded via the subject smartphone/use of trial application. Subjects will also be asked to rate their average pain level (NRS scale) over the past hour and the past 12 hours in the morning (8-10 am) and evening (8-10 pm) via the subject smartphone/use of trial application.

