7.1.2 Summarization by Visit

Data summarized by study visit will be based on the nominal, scheduled visit from the eCRF or tablet. Analysis visits will be labelled as Baseline or Day 1, Day 4, Day 14, and Day 28 in all table summaries.

Data collected for the last subject treatment visit completed will be summarized separately for:

- The scheduled Day 14 (End of Treatment) visit for those subjects who complete the scheduled end of study visit, per protocol. This summary will be labeled as “Day 14” in the analysis.
- The last visit completed on-study, combining data collected for subjects who complete the Day 14 (End of Treatment) visit as well as the early termination (ET) visit for those subjects who discontinue the study early. This summary will be labeled as “Day 14/ET” in the analysis.

For assessments collected daily on the smartphone/trial application, visits will be summarized based on the study day relative to the date of treatment start for all data. However, statistical analyses will be conducted using Day 1 through 14 observations only.

Data collected at unscheduled visits will not be included in by-visit summaries, but will be considered when endpoint derivations potentially include multiple visits (e.g., determination of baseline value, determination of worst post-baseline value, etc.). All data will be included in subject listings.

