7.1.3 Baseline Value

For analyses listed in this SAP, the baseline value is defined as the last measurement reported prior to the first dose of study drug, unless otherwise noted.

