7.4.4 Primary Efficacy Endpoint Analysis Methods

The primary efficacy endpoint is NRS subject-rated pain “right now” due to acute back spasm on Day 14 for all subjects in the ITT population. This analysis will be performed using a linear test of trend across all tolperisone doses.

The null and alternate hypotheses to be tested are:

H₀: There is no significant trend in NRS rating of pain “right now” across dose groups

H₁: There is significant trend in NRS rating of pain “right now” across dose groups

The linear test of trend will be performed using a mixed effect model for repeated measures (MMRM) using an unstructured covariance matrix to model within-patient errors. However, if the computational algorithm fails to converge, other covariance structures will be evaluated (e.g., compound symmetry). The covariance structure converging to the best fit, as determined by Akaike’s information criterion, will be used. The Kenward and Roger method will be used to calculate the denominator degrees of freedom for the test of fixed effects. Based on this model, the hypothesis test described above will be tested using a two-sided test at the $\alpha=0.05$ level of significance.

The response variable will be the observed NRS rating of pain “right now”. The observed value on Day 14 is the primary time point of interest. The model will include factors for treatment group (5 levels: placebo, 150 mg/day, 300 mg/day, 450 mg/day and 600 mg/day) and visit (three levels: Day 1/Baseline, Day 4, and Day 14) as fixed effects, the treatment by visit interaction, and the baseline NRS rating as a covariate. The primary analysis will be based on all available data without imputation. Day 14 will reflect subjects that have completed the scheduled Day 14 (Visit 3). Subjects discontinuing the study may be analyzed as part of the sensitivity analysis using data imputation methods (LOCF and Multiple Imputation) to address missing data.

The observed NRS rating and change from baseline values will be presented using descriptive statistics for each treatment group by visit. The p-value for the overall test of trend on Day 14 will be presented. The pairwise least-square mean (LSM) estimates and least-square mean differences (LSMD) for each tolperisone dose level versus placebo will also be presented with 95% confidence intervals of the LSMD and associated p-values for the Day 14 visit observed values.

A plot of NRS subject rating of pain right now across study days will be presented.

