7.4.5 Secondary Endpoint Analysis Methods

7.4.5.1 NRS Rating of pain “right now” on Day 4

Analysis performed for the primary endpoint will be repeated for the NRS at Day 4 using the same MMRM model. Contrast and estimate statements will be used in the primary model to analyze the Day 4 values.

7.4.5.2 NRS Rating of pain over past 1 hour and 12 hours on Days 1 through 14

NRS subject rating of pain over past 1 hour and 12 hours is collected daily as AM and PM assessments. The AM, PM and average of AM/PM values will be summarized descriptively by study day for each treatment group. Summaries for the 1 hour assessment and 12 hours assessment will be presented separately.

An MMRM model using a linear test of trend will be performed similar to the primary endpoint. The model will include response as the average of the AM and PM NRS rating over past 1 hour or 12 hours and factors for treatment group (5 levels: placebo, 150 mg/day, 300 mg/day, 450 mg/day and 600 mg/day) and visit (14 levels: Day 1 to Day 14) as fixed effects and the treatment by visit interaction.

The pairwise least square mean (LSM) estimates and least-square mean differences (LSMD) for each tolperisone dose level versus placebo will be presented with 95% confidence intervals of the LSMD and associated p-values for the Day 14 visit. The p-value for the overall test of trend on Day 14 will also be presented.

Plots of NRS subject rating of pain due to back spasm over past 12 hours and past 1 hour will be plotted with the average of the AM and PM assessments on the y-axis and study day on x-axis.

7.4.5.3 NRS Rating of pain at rest and on movement on Days 1 through 14

NRS subject rating of pain at rest and with movement collected once daily in the evening for the 14 day treatment period. The observed values will be summarized descriptively by study day for each treatment group. Summaries for the at rest assessment and with movement assessment will be presented separately.

An MMRM model using a linear test of trend will be performed similar to the primary endpoint. Plots of NRS subject rating of pain at rest and with movement across study days will be presented.

7.4.5.4 *Subject Rating of Medication Helpfulness*

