SRMH values will be summarized categorically by treatment group for Days 4 and 14 for the ITT Population. The frequency and percentage of subjects in each response category will be presented. The comparison of each group to placebo will be conducted using a Wilcoxon Rank Sum test for the Day 14 values and p-values presented.

7.4.5.5 *Fingers to Floor Distance*

Fingers to floor distance will be assessed at Baseline, Day 4, and Day 14 and will be analyzed using a linear test of trend similar to the primary endpoint on Day 14. Pairwise estimates of the observed value will be presented.

7.4.5.6 *Global Symptom assessments (CGI and PGI)*

Global symptom assessments will be summarized by treatment group for the ITT population. CGI-S and PGI-S will be assessed at the baseline visit only. CGI-C and PGI-C will be assessed at Day 4 and Day 14. The frequency and percentage of subjects in each response category at Baseline, Day 4 and Day 14 will be presented. The comparison of each group to placebo will be conducted using a Wilcoxon Rank Sum test for the Day 14 values and p-values presented.

7.4.5.7 *Quality of Sleep*

Quality of sleep will be analyzed using the same methods described for the global symptom assessments in section 7.4.5.6. The comparison of each group to placebo will be conducted using a Wilcoxon Rank Sum test for the Day 14 observed values.

7.4.5.8 *Time to Pain Relief*

Time to pain relief (days) will be assessed using the NRS assessment of subject rating of pain over the past 12 hours. NRS assessments on or after Day 2 will be considered for time to relief. The first post-baseline occurrence of an AM or PM 12-hour NRS score equal to 2 or lower (0 = no pain, 10 = worst possible pain) will be used as the criterion for relief.

Subjects who withdraw from the study prior to the end of treatment visit or who complete the treatment period without having met the criteria for relief will be censored at the time of their last NRS assessment. Time to relief will be presented in days as (date of relief/censoring – date of first dose + 1).

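### SAP 7.4.4 uses the Day 1 pain score both as a response and as the covariate, so the planned unstructured primary model has no maximum-likelihood solution

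*SAP*

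**What the plan says.** SAP 7.4.4 takes the observed NRS rating of pain 'right now' as the response, not the change from baseline. Besides treatment (five levels), the model terms are "visit (three levels: Day 1/Baseline, Day 4, and Day 14) as fixed effects, the treatment by visit interaction, and the baseline NRS rating"; the last of these is the covariate. No baseline-by-visit term is listed, so baseline has one slope. The within-patient covariance is unstructured. The fallback reads "if the computational algorithm fails to converge, other covariance structures will be evaluated (e.g., compound symmetry"), and the best-fitting structure by AIC is then used.

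Three other places fix what the covariate is:

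- SAP 7.1.3: "the baseline value is defined as the last measurement reported prior to the first dose of study drug".
- Protocol 12.1: 'right now' pain is rated "on Day 1 (baseline assessment) and on Days 4 (Visit 2) and 14 (Visit 3) during the clinic visit".
- Protocol 11.2.1 lists the 'right now' NRS under "The following baseline assessments will be conducted by the Investigator or designee prior to dosing on Day 1".

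SAP 7.1.2 adds that unscheduled data "will be considered when endpoint derivations potentially include multiple visits (e.g., determination of baseline value").

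Protocol 17.4.2.1 names time as a fixed effect and baseline as a covariate, but does not list Day 1 as a level of time. SAP 7.7.1, on changes in planned analyses, does not mention the addition.

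**The concern.** The Day 1 response and the baseline covariate are the same number for every subject who has only the scheduled pre-dose rating. The model can then predict all Day 1 responses exactly, and an unstructured matrix gives Day 1 its own variance, which can shrink to zero without limit. The planned fit has no solution to converge to.

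This model supplies the only primary trend test and the Day 14 dose-versus-placebo estimates. It also supplies the Day 4 analysis: "Contrast and estimate statements will be used in the primary model to analyze the Day 4 values". If the fit is degenerate, the reported standard error and p-value come from the software's stopping point or from whichever substitute covariance is chosen.

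**Working it through.** **The plan's own figure.** Table 1 gives 81% power for the linear contrast with standardised differences 0.1/0.2/0.3/0.4. With contrast (-2, -1, 0, 1, 2) and n = 80, the contrast is -0.1 + 0 + 0.3 + 0.8 = 1.0 and its SE is √(10/80) = 0.354. Power is Φ(1.0/0.354 - 1.96) = Φ(0.87) = 81%. The sample-size figures are not in dispute.

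**1. No maximum.** Let b be the Day 1 NRS, β the slope and σ₁² the Day 1 residual variance. Apart from group means, the Day 1 residual is (1 - β)b. At β = 1 with Day 1 group terms of 0, every Day 1 residual is 0. The REML criterion then contains (400 - 5 - 1) ln σ₁² = 394 ln σ₁², which has no lower bound. Each tenfold fall in σ₁² should lower -2 log-likelihood by 394 × ln 10 = 907.2. Fitted to simulated data (5 × 80), it was 1644, 737, -170 and -1077 at σ₁² = 1, 0.1, 0.01 and 0.001. Each step is 907. No assumed correlation is needed for this. A baseline-by-visit term would not cure it, because the Day 1 slope would still fit exactly.

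**2. If such a fit is accepted as converged.** The Day 14 contrast uses mean(Day 14) - β × mean(b), which tends to the change score as β tends to 1. The Day 14 variance is not pinned down in the same way. It equals a conditional variance plus γ²σ₁², where γ, the regression on the Day 1 residual, can grow like 1/(1 - β). Nothing ties σ₁² to (1 - β)². Nine runs of general-purpose optimisers on one simulated data set all gave an estimate of -1.23:

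| Reported status | Runs | SE | p |
|---|---|---|---|
| Success | 6 | 1.39 to 18.8 | 0.37 to 0.95 |
| Failure | 3 | 0.90 to 2.44 | 0.17 to 0.61 |

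On the same data the three common-variance structures gave p = 0.0145 to 0.0149. The model with Day 4 and Day 14 only gave p = 0.041.

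**3. If non-convergence is reported.** Structures with a separate Day 1 variance share the defect. Among common-variance structures, compound symmetry can be worked by hand. Write r₄ and r₁₄ for the correlations of baseline with Day 4 and Day 14, and s_b, s₄ and s₁₄ for the SDs. In large samples:

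- β = (1 + r₄s₄/s_b + r₁₄s₁₄/s_b)/3
- Day 1 residual variance = (1 - β)²s_b²
- Day k residual variance = s_k² + β²s_b² - 2βr_k s_b s_k
- the model's Day 14 variance is the mean of the three
- type I error = 2Φ(-1.96 × √(model variance/true Day 14 variance))

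Day 14 SD 2.0 is the planning value (Protocol 17.2, SAP 7.6). The other inputs are assumptions.

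| s_b, s₄; r₄, r₁₄ | β | Day 1, 4, 14 variances | Mean | SE ratio | Type I error | Simulated |
|---|---|---|---|---|---|---|
| 1.4, 2.0; 0.4, 0.3 | 0.667 | 0.22, 3.38, 3.75 | 2.45 | 0.81 | 11.3% | 11.4% |
| 1.2, 1.8; 0.7, 0.2 | 0.794 | 0.06, 1.75, 4.15 | 1.98 | 0.69 | 17.5% | 16.9% |
| 2.0, 2.5; 0.2, 0.7 | 0.650 | 0.49, 6.64, 2.05 | 3.06 | 1.22 | 1.7% | 1.9% |

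The last two rows are the extremes for compound symmetry over baseline SD 1.2 to 2.0, Day 4 SD 1.8 to 2.5 and correlations 0.2 to 0.7. When AIC chooses among compound symmetry, AR(1) and Toeplitz, the range is 0.8% to 17.5%. In three mid-range settings all three structures gave 10.1% to 10.8%, and a separate simulation of compound symmetry gave 13.1% in one assumed setting. With integer scores limited to the NRS range, compound symmetry gave 11.0%, 11.0% and 3.9%.

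**4. With Day 1 removed from the response.** The likelihood has a proper maximum. Simulated type I error was 4.1% to 4.2% (Monte Carlo SE up to about 1 point), and a Day 14 ANCOVA gave 4.8% to 5.5%. Power for the 0.1/0.2/0.3/0.4 pattern was 84% to 92%.

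**The case against.** The strongest reply is that the SAP does have a rule: a trigger (non-convergence) and a selector (AIC). That is fair, and the gap is narrower than an absence of pre-specification. The candidate list is open, and there is no instruction for a degenerate fit that the software reports as converged. Such a fit would also win any AIC comparison.

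A second reply is that unscheduled pre-dose ratings could make baseline differ from the Day 1 response. That would bound the likelihood but leave it nearly singular. With a 1-point difference in 4 or 20 of 400 subjects, the mean fitted slope was still 0.975 to 0.996. Type I error in the two settings simulated was 4.5% to 5.5%, but the documents plan no such second rating.

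A reader might infer that an accepted degenerate fit is harmless because it amounts to a change-score test at 5%. Only the point estimate behaves that way. At the same Day 1 variance there are fits with -2 REML log-likelihood about 60 lower and a contrast SE of about 5.0 to 5.2, against a change-score SE of 0.71. No type I error or power can be stated for this path.

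A reader might equally infer that the primary test is bound to be anti-conservative. The documents do not support that either. The level under a common-variance fallback falls on both sides of 5%, depending on SDs and correlations that they do not give.

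**Conclusion.** The model is wrong as written and should be corrected before unblinding. That the planned unstructured likelihood has no maximum follows from the text alone, given the single scheduled pre-dose rating, and no other section cures it.

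The size of the consequence is conditional. On one path the standard error is indeterminate. On the other the 5% level is not assured: about 1% to 17.5% over the assumed ranges, and about 10% to 13% in typical simulated settings. These figures assume complete data and the stated SDs and correlations. How often each value would arise cannot be said. SAS was not tested, and the documents do not show which path would occur, so this is not evidence that any reported result is inflated.

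**What to change.** In SAP 7.4.4, define the response visits as Day 4 and Day 14 only, and keep the Day 1 NRS as the baseline covariate. A baseline-by-visit interaction is optional. Keeping Day 1 as a response and dropping the covariate would also remove the degeneracy, but Protocol 17.4.2.1 specifies the covariate.

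Apply the same wording to fingers-to-floor distance. It has a Day 1 value and "will be analyzed using a linear test of trend similar to the primary endpoint on Day 14" (SAP 7.4.5.5), and SAP 7.4.6.1 extends the baseline adjustment to secondary repeated-measures models where a baseline is captured. The past-1-hour, past-12-hour, rest and movement models have no scheduled pre-dose rating, so they do not share the problem unless a pre-dose value is used as baseline.

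The cost is one sentence in the SAP and one program line before unblinding, with no new data or subjects.

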7.4.5 Secondary Endpoint Analysis Methods

7.4.5.1 NRS Rating of pain “right now” on Day 4

Analysis performed for the primary endpoint will be repeated for the NRS at Day 4 using the same MMRM model. Contrast and estimate statements will be used in the primary model to analyze the Day 4 values.

7.4.5.2 NRS Rating of pain over past 1 hour and 12 hours on Days 1 through 14

NRS subject rating of pain over past 1 hour and 12 hours is collected daily as AM and PM assessments. The AM, PM and average of AM/PM values will be summarized descriptively by study day for each treatment group. Summaries for the 1 hour assessment and 12 hours assessment will be presented separately.

An MMRM model using a linear test of trend will be performed similar to the primary endpoint. The model will include response as the average of the AM and PM NRS rating over past 1 hour or 12 hours and factors for treatment group (5 levels: placebo, 150 mg/day, 300 mg/day, 450 mg/day and 600 mg/day) and visit (14 levels: Day 1 to Day 14) as fixed effects and the treatment by visit interaction.

The pairwise least square mean (LSM) estimates and least-square mean differences (LSMD) for each tolperisone dose level versus placebo will be presented with 95% confidence intervals of the LSMD and associated p-values for the Day 14 visit. The p-value for the overall test of trend on Day 14 will also be presented.

Plots of NRS subject rating of pain due to back spasm over past 12 hours and past 1 hour will be plotted with the average of the AM and PM assessments on the y-axis and study day on x-axis.

7.4.5.3 NRS Rating of pain at rest and on movement on Days 1 through 14

NRS subject rating of pain at rest and with movement collected once daily in the evening for the 14 day treatment period. The observed values will be summarized descriptively by study day for each treatment group. Summaries for the at rest assessment and with movement assessment will be presented separately.

An MMRM model using a linear test of trend will be performed similar to the primary endpoint. Plots of NRS subject rating of pain at rest and with movement across study days will be presented.

7.4.5.4 *Subject Rating of Medication Helpfulness*

SRMH values will be summarized categorically by treatment group for Days 4 and 14 for the ITT Population. The frequency and percentage of subjects in each response category will be presented. The comparison of each group to placebo will be conducted using a Wilcoxon Rank Sum test for the Day 14 values and p-values presented.

7.4.5.5 *Fingers to Floor Distance*

Fingers to floor distance will be assessed at Baseline, Day 4, and Day 14 and will be analyzed using a linear test of trend similar to the primary endpoint on Day 14. Pairwise estimates of the observed value will be presented.

7.4.5.6 *Global Symptom assessments (CGI and PGI)*

Global symptom assessments will be summarized by treatment group for the ITT population. CGI-S and PGI-S will be assessed at the baseline visit only. CGI-C and PGI-C will be assessed at Day 4 and Day 14. The frequency and percentage of subjects in each response category at Baseline, Day 4 and Day 14 will be presented. The comparison of each group to placebo will be conducted using a Wilcoxon Rank Sum test for the Day 14 values and p-values presented.

7.4.5.7 *Quality of Sleep*

Quality of sleep will be analyzed using the same methods described for the global symptom assessments in section 7.4.5.6. The comparison of each group to placebo will be conducted using a Wilcoxon Rank Sum test for the Day 14 observed values.

7.4.5.8 *Time to Pain Relief*

Time to pain relief (days) will be assessed using the NRS assessment of subject rating of pain over the past 12 hours. NRS assessments on or after Day 2 will be considered for time to relief. The first post-baseline occurrence of an AM or PM 12-hour NRS score equal to 2 or lower (0 = no pain, 10 = worst possible pain) will be used as the criterion for relief.

Subjects who withdraw from the study prior to the end of treatment visit or who complete the treatment period without having met the criteria for relief will be censored at the time of their last NRS assessment. Time to relief will be presented in days as (date of relief/censoring – date of first dose + 1).

The number of subjects with relief and those censored will be summarized by treatment group for the ITT population. Estimates of the median times will be presented along with their associated 95% confidence intervals. Treatment group comparisons will be summarized with hazard ratios and their associated 95% CI from a Cox Proportional Hazards regression model with treatment as the main effect and p-values from a generalized Wilcoxon test.

The Kaplan Meier plots of time to pain relief by treatment group will be presented and display the subjects with relief and those censored at each study day.

A by subject listing of derived time to relief estimates will also be presented.

7.4.5.9 *Rescue Medication Use*

The use of study provisioned medication will be summarized using frequency counts and percentages for the number of tablets consumed by treatment group for the ITT population. Descriptive statistics will also be presented by treatment group. The number of days of medication use, average daily use (caplets/day of medication use) and total use will be tabulated using descriptive statistics. The frequency and percentage of subjects with rescue medication entry will be presented.

The Shapiro-Wilk test will be used to examine the assumption of normality for total rescue medication use across all dose groups. If this test is statistically significant (i.e., $p \leq 0.05$) then the assumption of normality is violated and the total rescue medication consumption will be analyzed using a Wilcoxon Rank Sum test.

However, if the assumption of normality holds (i.e., Shapiro-Wilk p-value > 0.05), then the total rescue medication consumption will be analyzed using an analysis of variance (ANOVA) model with randomized treatment as the main effect. The LSM and LSMD will be presented with associated 95% CI and p-values comparing each treatment group to placebo.

A data listing of rescue medication use will be presented and include the average number of tablets consumed and total number of tablets rescue medication consumed for each subject.

7.4.5.10 *Oswestry Disability Index*

ODI score (%) will be calculated as $(\text{total score} \times 2) / (\text{number of sections answered} / 10)$, rounded to the nearest integer, where the total score is the sum of the individual section scores.

Observed ODI score and change from baseline will be summarized descriptively for each treatment group for the ITT population. Each dose group will be compared to placebo using an ANCOVA model with observed value as the response, main effects for treatment group and a covariate adjusted for the baseline ODI score. The LSM, LSMD, 95% CI and p-values will be presented at Day 14.

Individual section scores will be summarized separately for the ITT population by treatment group. The frequency and percentage of subjects in each response category at Baseline, Day 4 and Day 14 will be presented. The comparison of each group to placebo will be conducted using a Wilcoxon Rank Sum test for the Day 14 values and p-values presented.

7.4.5.11 *Visual Analogue Scale of Sleepiness*

The Day 4 VAS ratings of sleepiness will be summarized descriptively by treatment group for the ITT population. Each dose group will be compared to placebo using an ANOVA model with the observed values as the response and main effects for treatment group. The LSM, LSMD, 95% CI and p-values will be presented.

7.4.5.12 *Daily Activities*

Daily activity scores will be summarized categorically for Days 1 to 14 by treatment group for the ITT population. The frequency and percentage of subjects in each response category will be presented. The comparison of each group to placebo will be conducted using a Wilcoxon Rank Sum test for the Day 14 values and p-values presented.

7.4.6 *Statistical/Analytical Issues*

7.4.6.1 *Adjustments for Covariates*

The MMRM model to test for linear trend for the primary endpoint will include a covariate adjustment for the baseline value. Secondary endpoints utilizing an MMRM will be analyzed similarly when a baseline value is captured.

7.4.6.2 *Handling of Dropouts or Missing Data*

Primary and secondary endpoints including all NRS assessments (right now, past 12 hours, past 1 hour, at rest, on movement), Fingers to floor Distance, Clinician's Global Impression, and Oswestry Disability Index assessments will be analyzed using both observed data and data imputed using last observation carried forward (LOCF), if the dropout rate is $\geq 5\%$ (20/400 subjects). In the LOCF method, the most recent non-missing value for the endpoint is carried forward to replace a missing value at a post-baseline visit within a subject. Baseline values will not be carried forward.

Methods for multiple imputation (MI) for missing data may be explored for endpoints if the dropout rate is $\geq 15\%$ (60/400 subjects).

7.4.6.3 *Interim Analyses and Data Monitoring*

There are no interim analyses planned, nor is there a plan to establish a data monitoring committee for this study.

7.4.6.4 *Multicenter Studies*

This is a multicenter study, with approximately 45 sites expected to participate. Efficacy data collected from all study sites will be pooled for data analysis. The effect of study site on the efficacy analysis results may be explored post-hoc, as needed.

7.4.6.5 *Multiple Comparisons/Multiplicity*

There will be no adjustments for multiple comparisons in the efficacy analysis for this study. All of the above analyses will be conducted using two-sided tests at the $\alpha = 0.05$ level of significance.

7.4.6.6 *Use of an “Efficacy Subset” of Subjects*

The primary efficacy analysis will be performed on the ITT population; the PP population will be utilized as a sensitivity analysis for the primary endpoint and secondary endpoints, including NRS (right now, past 12 hours, past 1 hour, at rest, on movement), Subject Rating of Medication Helpfulness, Fingers to Floor Distance, Clinician’s Global Impression assessments, and Oswestry Disability Index. The PP population will exclude subjects with major protocol violations.

7.4.6.7 *Active-Control Studies Intended to Show Equivalence*

This study does not include an active-control product and is not intended to demonstrate equivalence between any two drug products.

7.4.6.8 *Examination of Subgroups*

There are no planned analyses to assess efficacy results by subgroups.

7.4.7 *Plasma Concentrations*

Plasma concentration measurements will be summarized in a separate report and is outside the scope of this SAP.

7.4.8 *Pharmacokinetic Analysis*

Pharmacokinetic analysis will be summarized in a separate report and is outside the scope of this SAP.

7.5 **Safety Evaluation**

Safety analysis will be carried out for the Safety Population, which will include all subjects who receive at least one dose of study drug. Subjects who do not complete the study, for whatever reason, will have all available data up until the time of termination included in the analysis. For safety analysis presented by study visit, the baseline value will be defined as the last value reported prior to first study drug administration. All analyses will be presented by treatment group.

7.5.1 *Extent of Exposure*

Extent of exposure to study treatment will be summarized for the Safety Population by treatment group. The date of first and last dose is collected on the eCRF. If missing, subjects’ dosing eDiary data will be used to determine dates of first and last doses. The duration of exposure will be presented in days and calculated as the date of last dose of study drug minus the date of first dose of study drug, plus one. Duration of exposure, average dose received, and total dose received (mg) will be summarized using descriptive statistics.

Total dose received will be derived based on the number of tablets returned at the end of treatment visit and the actual dose (mg) received. Average dose will be calculated as the total

dose divided by the duration of exposure. The planned number of doses for each subject is 42 (14 days of TID dosing).

7.5.2 *Adverse Events*

Treatment-emergent adverse events (TEAEs) are defined as those adverse events (AEs) with onset on or after the first dose of study drug through 24 hours after the last dose of study drug. Existing events that worsened during this period will also be considered treatment emergent. If start time is not available, AEs with onset between the date of the first dose through the day after the date of last dose (+1 day) will be considered treatment-emergent.

Adverse events with onset greater than 24 hours (or >1 day) after the date of the last dose of study drug through the date of the follow-up visit (Visit 4/Day 28) will be considered after-treatment events.

Treatment-emergent and after-treatment AEs will be summarized by treatment group. Events reported with a partial onset date (e.g., month and year are reported but the day is missing) will be considered to be treatment-emergent if it cannot be confirmed that the event onset was prior to the first dose of study drug based on the available date entries.

Verbatim terms on case report forms will be mapped to preferred terms and system organ classes using the Medical Dictionary for Regulatory Activities (MedDRA, version 21.1).

Summaries that are displayed by system organ class and preferred terms will be ordered by descending incidence of system organ class and preferred term within each system organ class. Summaries displayed by preferred term only will be ordered by descending incidence of preferred term. Summaries of the following types will be presented:

- Overall summary of number of unique TEAEs and treatment-emergent serious adverse events (SAEs) and subject incidence of TEAEs meeting various criteria;
- Subject incidence of TEAEs by MedDRA system organ class and preferred term;
- Subject incidence of TEAEs by MedDRA preferred term;
- Subject incidence of TEAEs by severity grade, MedDRA system organ class, and preferred term;
- Subject incidence of TEAEs by relationship to study drug, MedDRA system organ class, and preferred term;
- Subject incidence of SAEs by MedDRA system organ class and preferred term;
- Subject incidence of TEAEs Leading to Study Drug Discontinuation by MedDRA system organ class and preferred term; and
- Subject incidence of TEAEs by CYP450 2D6 Genotype, MedDRA system organ class and preferred term.

- Subject incidence of After-treatment Adverse Events by MedDRA preferred term.

At each level of summarization (e.g., any AE, system organ class, and preferred term), subjects experiencing more than one AE will be counted only once. In the summary of TEAEs by severity grade, subjects will be counted once at the highest severity reported at each level of summarization; in the summary of TEAEs by relationship, subjects will be counted once at the closest relationship to study drug. Related events include those reported as “Possibly Related” or “Definitely Related” to study drug; events considered not related are those reported as “Unrelated” to study drug.

Adverse event data will be presented in data listings by patient, treatment group, and event. The study phase (e.g., treatment-emergent, after-treatment) will also be presented in the listing. Serious AEs and AEs leading to discontinuation, interruption or dose reduction, interruption of the study drug will be presented in separate data listings.

